**Safety:**

The primary safety outcome is hospital readmission. We will employ a Bayesian safety monitoring rule to stop the study if  $\Pr(\pi_{5day} - \pi_{control} > 0.05) > 0.9$  where  $\pi_{5day}$  is the true rate of hospital readmission under the 5 day protocol and  $\pi_{control}$  is the rate under standard of care. The rule means we will stop the study if there is high posterior probability (greater than 90%) that the readmission rate is 5% higher with the 5 day protocol than under standard of care. Over the last 1000 cases, the rate of readmission under standard care is 15%. We assume prior distributions of  $\pi_{5day} \sim \text{Beta}(0.2, 0.8)$  and  $\pi_{control} \sim \text{Beta}(15, 85)$ . That is, we assume the rate in under the 5 day protocol is higher, but with fairly high uncertainty, and we assume 15% under control equivalent to information from 100 subjects. Posterior probabilities will be calculated at the time of the interim efficacy analysis and every 12 patients thereafter. Stopping rules at the interim analysis (36 patients per group) are shown below:

Readmissions in Standard of Care (out of 36)	Stop if Readmissions in 5 day arm are $\geq$ (out of 36)
1-2	10
3-5	11
6-8	12
9-12	13

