#### **1.6 Dose Rationale and Risk/Benefits**

The major risks for this research are the development of postoperative complications in the outpatient setting, where identification of these complications may be delayed. The risk of fall due to early mobilization with physical therapy, and the potential for dehydration if patients are not able to tolerate adequate oral intake to maintain hydration at home following discharge. Specific measures to minimize these risks are detailed in the next question. Additional risks include violation of loss of confidentiality or violations in protecting personal health information.

The risk of a delayed diagnosis of postoperative complications will be mitigated with increased outpatient communication including daily phone calls and liberalized use of visiting nursing services and outpatient physical therapy. The risk of falls due to early mobilization will be mitigated by having physical therapy

and/or occupational therapy staff present at all additional therapy sessions beyond our current 7 day standard. The risk of dehydration will be mitigated by frequent daily phone contact by a highly-qualified nurse practitioner in the postoperative outpatient setting. Standard protocols as detailed above will be in place to protect patient PHI.

Patients in the study will benefit from increased and standardized physical and occupational therapy services in the postoperative setting, potential for improved pain control through the use of multimodal therapy, and increased preoperative and postoperative outpatient support by a highly-qualified service-specific nurse practitioner.

Decreased length of hospital stay and increased support (as detailed above) may prove to reduce the rate of overall complications and will allow patients return home quicker. Additional benefit may come in the form of reduced overall cost of care.

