### **3.4 Primary Safety Endpoints**

*Perioperative complications, morbidity, mortality, and hospital readmission will all be tracked*

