**Secondary outcomes:**

Differences among treatment groups with respect to secondary continuous outcomes (post-operative median length of stay, cost) will be assessed using two-sample t-tests or Wilcoxon rank sum tests. Differences in binary outcomes (readmission rate, post-operative complications, delayed gastric emptying, anastomotic leaks, intra-abdominal abscesses, wound infection, urinary tract infection, respiratory compromise, renal failure) will be assessed using Chi-square tests or Fisher's exact test)

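### The only numerical safety stopping rule counts readmissions alone, so a patient who dies without being readmitted is scored as event-free, and mortality has no threshold or planned comparison

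*Combined protocol and SAP*

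**What the plan says.** Section 3.4 (Primary Safety Endpoints) reads: "Perioperative complications, morbidity, mortality, and hospital readmission will all be tracked". The Safety paragraph of section 7.2 narrows this: "The primary safety outcome is hospital readmission". The stopping criterion there is Pr(π_5day − π_control > 0.05) > 0.9, and the plan glosses it as follows: "The rule means we will stop the study if there is high posterior probability (greater than 90%) that the readmission rate is 5% higher". The priors are Beta(0.2, 0.8) for the 5-day arm and Beta(15, 85) for control; for the latter, "we assume 15% under control equivalent to information from 100 subjects". On timing: "Posterior probabilities will be calculated at the time of the interim efficacy analysis and every 12 patients thereafter". The table is introduced by "Stopping rules at the interim analysis (36 patients per group) are shown below" and is laid out as readmissions out of 36 in each arm. No time window for readmission is given.

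Section 8.4 refers back to the statistical plan for all stopping rules, so this is the only numerical rule for harm. Mortality is absent from the secondary endpoints (section 3.3) and from the planned comparisons (section 7.2, Secondary outcomes). That same paragraph compares "post-operative median length of stay, cost" by t-test or Wilcoxon test and does not say how an in-hospital death is handled. Section 7.3 removes anyone with missing length of stay from every analysis.

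**The concern.** Section 1.6 names as a major risk of the research "postoperative complications in the outpatient setting, where identification of these complications may be delayed", and section 5.3 repeats it. The gravest form of that risk is a death before the patient can be readmitted. Death also competes with readmission, because a patient who has died can no longer be readmitted. Under the rule as written, such a patient gets the same score as one who recovers uneventfully at home. A patient who dies during the index stay can never be readmitted and is scored the same way. If these deaths are more frequent in the 5-day arm, the rule sees less harm than there is and may let the trial continue when a count of all serious failures would stop it.

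**Working it through.** **Inputs.** From section 7.2, Safety: the two priors, the 0.05 margin, the 0.9 cut-off, and 36 patients per arm at the first look. The documents give no mortality rate, so every death count or death rate below is an assumption.

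**Formula.** With x events in the 5-day arm and y in control, the posteriors are π_5day ~ Beta(0.2 + x, 0.8 + 36 − x) and π_control ~ Beta(15 + y, 85 + 36 − y). Stop if Pr(π_5day − π_control > 0.05) exceeds 0.9.

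**Reproducing the plan's table.** The smallest x that stops is 10 for y = 1–2, 11 for y = 3–5, 12 for y = 6–8 and 13 for y = 9–12. All four rows agree with the plan, so the table is a correct calculation for readmission. The point concerns what is counted.

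**Effect of unreadmitted deaths, with y = 5.** The control posterior is Beta(20, 116). Deaths are assumed in the 5-day arm only, and the priors are kept as stated.

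| 5-day arm | As written | Deaths counted as events |
|---|---|---|
| 10 readmitted + 1 death | x = 10, Beta(10.2, 26.8): 0.841, continue | x = 11, Beta(11.2, 25.8): 0.910, stop |
| 8 readmitted + 1 death | x = 8, Beta(8.2, 28.8): 0.612, continue | x = 9: 0.741, continue |
| 8 readmitted + 2 deaths | 0.612, continue | x = 10: 0.841, continue |
| 8 readmitted + 3 deaths | 0.612, continue | x = 11: 0.910, stop |

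The first row lies exactly at the boundary. If control also had one such death, the composite would be 11 v 6, which gives 0.891 and continues.

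**Chance of stopping at the first look.** This is the sum over y of Bin(y; 36, p_c) × Pr(X ≥ limit(y)), with X ~ Bin(36, p_5). The limits are those of the table, extended by the same criterion to values of y that it does not list. For the composite, p is the readmission rate plus the rate of death without readmission.

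| Readmission, control / 5-day | Assumed unreadmitted deaths, control / 5-day | As written | Deaths counted |
|---|---|---|---|
| 15% / 30% | 0 / 0.5% | 0.469 | 0.494 |
| 15% / 30% | 0 / 1% | 0.469 | 0.519 |
| 15% / 30% | 0 / 3% | 0.469 | 0.617 |
| 15% / 30% | 1% / 3% | 0.469 | 0.601 |
| 15% / 30% | 3% / 3% | 0.469 | 0.570 |
| 15% / 25% | 0 / 1% | 0.230 | 0.273 |
| 15% / 25% | 0 / 3% | 0.230 | 0.368 |
| 15% / 20% | 0 / 1% | 0.072 | 0.095 |

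The row with 3% deaths in both arms needs care. The true difference is still 15 points, yet the chance of stopping rises. At least part of the rise comes from keeping a control prior built for readmission alone. With a true control composite rate of 18%, the expected posterior mean is (15 + 0.18 × 36)/136 = 21.48/136 = 0.158. A composite therefore needs its own control prior.

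**The case against.** The strongest reply is that deaths are not left unwatched. Mortality is tracked (section 3.4), fatal events are serious adverse events, and adverse events are followed to 90 days after surgery or the end of the index stay if later (section 8.1). Under section 8.5.1, unexpected treatment-related deaths go to the IRB and the DSMC within 24 hours, and deaths judged unrelated must be reported within 5 days. The Medical Monitor can prompt an ad hoc DSMC meeting or recommend suspension or termination. For a rare, grave event this route can act on one death without waiting for the 72-patient look. All of that stands, so a reader who infers that safety as a whole is judged on readmission alone goes too far; that is true only of the numerical rule. But case review makes no between-arm comparison. Section 8.5.1 also declares common complications unrelated to the pathway and keeps them from the DSMC, which prejudges the cause of a death that follows one.

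A reader might make two further inferences.

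- **That a death is credited as a short stay or as a primary success.** The plan does not say so. An in-hospital death is not a discharge by POD 5, so on plain wording it is a failure. A death after discharge leaves the recorded index stay correct. Even if deaths by POD 5 in the 5-day arm alone were counted as discharges, an assumed 3% of them would raise the chance of a significant result under no effect only from 2.1% to 4.3%. The one real gap is an early in-hospital death in the secondary length-of-stay test. It could be entered as a short stay or dropped as missing under section 7.3; the plan does not say which.
- **That the omission always favours the 5-day arm.** It does so only if unreadmitted deaths are more frequent there. A control patient who dies unreadmitted likewise adds nothing to the control count.

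**Conclusion.** The concern holds for the stopping rule. Followed as written, it scores death without readmission as no event, and mortality, though listed in section 3.4, has neither a threshold nor a planned comparison. The size depends on mortality, which the documents do not give. With control readmission 15%, 5-day readmission 30% and deaths in the 5-day arm only, counting deaths raises the chance of stopping at the first look from 0.47 to 0.52 at 1% deaths, a small change, and to 0.62 at 3%. With 3% in both arms it is 0.57, still using the readmission-only control prior. The change is worth making because it puts the gravest outcome into the one rule that compares harm between arms, using data that are already collected. The primary endpoint is not affected.

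**What to change.** In section 7.2:

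1. Define the monitored safety event as readmission or death from any cause, over one stated window that is the same in both arms. Adverse events are already followed to 90 days, so a window up to that length needs no new follow-up.
2. Take the control prior for this composite from the same 1000 historical cases that gave the 15% readmission rate, and re-derive the stopping table from it. The present prior and table should not simply be carried over.
3. Add mortality by arm to the planned comparisons.
4. For the secondary length-of-stay comparison, use the Wilcoxon test with in-hospital deaths given the worst rank, so that an early death can be neither entered as a short stay nor dropped as missing.

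The primary endpoint needs no change. The cost is SAP wording, one re-read of the historical data, and a slightly different prior and table. No new data on trial patients are needed.

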#### Primary Outcome:

Randomization arms will be compared with respect to the primary outcome, proportion of patients discharged on postoperative day 5 using Fisher's Exact test. One interim analysis for efficacy will be performed when 72 patients have been randomized and completed follow-up for the primary outcome. The study will stop for efficacy if the p-value of the Fisher's exact test is less than 0.00506 at the interim analysis. Assuming the efficacy bound is not met, the null hypothesis will be rejected at the final analysis if the p-value is less than 0.04553.

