We propose to submit to the DSMC for review all AE/SAE’s specifically related to the WARP protocol interventions. These include, renal injury related to the volume restriction, injury related to enhanced physical therapy such as a fall, intolerance of the intervention (full liquid) diet with dizziness or lightheadedness. Given the fact that more than 50% of all pancreaticoduodenectomy patients develop some postoperative complication, such as pancreatic fistula, delayed gastric emptying, intraabdominal abscess, wound infection, urine infection, heart attacks, arrhythmias, pulmonary complications, renal, strokes, and deep vein thrombosis, and that these bear no relation to the specific interventions of the WARP protocol, they will not be reported to the DSMC.

	Grade 1	Grade 2	Grade 2	Grade 3		Grade 3		Grades 4 and 5
	Unexpected and Expected	Unexpected	Expected	Unexpected with Hospitalization	Unexpected without Hospitalization	Expected with Hospitalization	Expected without Hospitalization	Unexpected and Expected
Unrelated Unlikely	Reviewed at	Reviewed at	Reviewed at	5 Working Days	Reviewed at Quarterly	5 Working Days	Reviewed at Quarterly	Phase 1 - 48 Hours

	Quarterly DSMC Meeting and IRB Annual Review	Quarterly DSMC Meeting and IRB Annual Review	Quarterly DSMC Meeting and IRB Annual Review		DSMC Meeting and IRB Annual Review		DSMC Meeting and IRB Annual Review	(Death: 24 Hours)  Phase 2 - 5 Working Days
Possible Probable Definite	Reviewed at Quarterly DSMC Meeting and IRB Annual Review	5 working days	Reviewed at Quarterly DSMC Meeting and IRB Annual Review	48 Hours (Death: 24 Hours)	Phase 1 - 48 Hours  Phase 2 - 5 Working Days	48 Hours (Death: 24 Hours)	Reviewed at Quarterly DSMC Meeting and IRB Annual Review	Phase 1 and Phase 2 - 48 Hours (Death: 24 Hours)

**\*\*NOTE:** This table is based on the NCI AE/SAE reporting Guidelines and the TJU IRB Policy and Procedures. Please follow the individual protocol AE/SAE reporting guidelines if more stringent reporting procedures are specified.

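### The Bayesian readmission rule is first applied at 72 patients; starting the same rule at 48 or 36 would stop a harmful pathway sooner at small cost

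*Combined protocol and SAP*

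**What the plan says.** The Safety part of section 7.2 sets the rule: "we will stop the study if there is high posterior probability (greater than 90%) that the readmission rate is 5% higher" in the 5-day arm than under standard care. The first evaluation is tied to efficacy: "Posterior probabilities will be calculated at the time of the interim efficacy analysis", and it is repeated "every 12 patients thereafter". The Primary Outcome part of the same section fixes the date: "One interim analysis for efficacy will be performed when 72 patients have been randomized and completed follow-up for the primary outcome". The stopping table confirms the size of that look: "Stopping rules at the interim analysis (36 patients per group) are shown below".

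Section 8.4 only refers back to the statistical plan. Section 8.5 provides a Medical Monitor and quarterly DSMC meetings, with no numerical readmission criterion. For a list of common postoperative complications that the protocol regards as unrelated to the interventions, section 8.5.1 says "they will not be reported to the DSMC".

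**The concern.** Sections 1.6 and 5.3 name, as the main risk of the research, complications that arise after discharge and are recognised late. Readmission is the outcome most likely to show this. The Safety text itself assumes a higher readmission rate in the 5-day arm, with considerable uncertainty. Yet the only formal comparison of readmission between arms starts at the halfway point, and the documents give no reason for tying it to the efficacy interim. A beta-binomial posterior can be computed at any sample size, so the method does not require the wait. At stake is the number of patients assigned to a harmful pathway before the rule is allowed to act.

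**Working it through.** **Inputs from the plan (section 7.2 Safety unless noted).** Stop if Pr(π5 − πc > 0.05) > 0.90. The 5-day prior is Beta(0.2, 0.8). The control prior is Beta(15, 85): "we assume 15% under control equivalent to information from 100 subjects". On past cases, "the rate of readmission under standard care is 15" per cent. The first look is at 36 per arm, then every 6 per arm. The maximum is 71 per arm (section 7.1); the Study Summary has 69.

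**Assumptions, not in the plan.** True 5-day rates of 20% to 40%, a true control rate of 15%, equal numbers per arm at each look, readmission status known at once, and stopping for safety only.

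**Step 1. Timing.** 72/142 = 51% of enrolment (72/138 = 52% on the Study Summary total). If accrual is even over the 3-year study, 72/142 × 36 months ≈ 18 months.

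**Step 2. Reproduce the stopping table.** With *a* readmissions of *n* in the 5-day arm and *c* of *n* in control:

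- π5 | data ~ Beta(0.2 + a, 0.8 + n − a)
- πc | data ~ Beta(15 + c, 85 + n − c)

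Example: n = 36, c = 5, a = 11 gives Beta(11.2, 25.8) and Beta(20, 116). Integrating numerically, Pr(π5 − πc > 0.05) = 0.91, so the study stops. With a = 10 it is 0.84, so it continues. Over all control counts in the table, the smallest stopping counts are 10, 11, 12 and 13 for 1–2, 3–5, 6–8 and 9–12 control readmissions, exactly as printed.

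**Step 3. Move only the first look.** Simulation of at least 60,000 trials per scenario, with the same priors, threshold and spacing, and the first look at 36 (plan), 24 or 18 per arm. Enrolment in the 5-day arm is counted as the maximum if the rule never stops the trial.

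| True 5-day rate | Mean 5-day-arm enrolment: 36 / 24 / 18 | Saving: 24 / 18 | Chance the rule stops: 36 / 24 / 18 |
|---|---|---|---|
| 15% (no harm) | 70.4 / 69.7 / 69.3 | – | 2.0% / 3.3% / 4.0% |
| 20%* | 65.4 / 63.2 / 62.1 | 2.2 / 3.3 | 14.2% / 17.1% / 18.4% |
| 25% | 59.3 / 54.8 / 52.7 | 4.5 / 6.6 | 42.3% / 45.8% / 47.2% |
| 30% | 49.5 / 42.7 / 40.0 | 6.7 / 9.4 | 73.6% / 75.6% / 76.3% |
| 35% | 41.9 / 33.3 / 29.7 | 8.6 / 12.2 | 91.9% / 92.7% / 93.1% |
| 40% | 38.0 / 27.9 / 23.6 | 10.1 / 14.4 | 98.4% / 98.6% / 98.8% |

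*Row computed with a maximum of 69 per arm; with 71 the savings are 2.2 and 3.5. Savings are taken before rounding. Repeat runs at 30% gave 9.4 to 9.8 for the start at 18 per arm. The choice of 69 or 71 changes the savings by no more than about 0.3 patient. Counting both arms roughly doubles each saving.

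**Step 4. Where the gain comes from.** At 30% v 15%, the rule stops 47% of trials before 72 patients if it starts at 24 per arm and 50% if it starts at 18; under the plan the figure is zero. The overall chance of stopping hardly changes (74% to 76%). The gain is in earliness and adds very little detection.

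**Step 5. Delay.** If 6 more patients per arm enrol before each decision, mean enrolment at 30% v 15% becomes 53.9 / 47.4 / 44.6, a saving of 6.5 or 9.3. Absolute exposure rises under every schedule, but the difference barely moves.

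**The case against.** Waiting for 36 per arm is a defensible choice. The 5-day prior weighs as much as one patient (0.2 + 0.8), so an early look rests on few events: at 18 per arm, 6 or 7 readmissions stop the trial when control has 0 to 6. Starting there doubles the false-stop chance. It also raises the chance of stopping at 20% v 15%, a difference that does not exceed the rule's own margin, from 14% to about 18%. These costs are real and must be stated with the proposal; starting at 24 per arm reduces both.

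A reader might infer that patients have little protection in the first half. The documents do not support that. Under section 8.5.1 the Medical Monitor reviews reportable events in real time and can recommend suspension, and an ad hoc DSMC meeting can be called. Under section 8.5.2 the DSMC meets quarterly, sees outcome results and votes on study status. The planned rule itself stops about 74% of trials at 30%. What remains true is narrower: none of these reviews has a numerical between-arm readmission criterion.

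A reader might also infer from section 8.5.1 that readmissions are hidden from the DSMC. The excluded list names complications and does not mention readmission. The same section says that all adverse events go to the DSMC, and its reporting table covers unrelated events with hospitalization. Those statements need reconciling, but that is a separate matter.

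Finally, a flat claim of about 10 patients spared would overreach. It needs a doubled readmission rate and a start at 18 per arm.

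**Conclusion.** The point holds as a cheap improvement to a design choice. The rule is coherent and its table is correct, but it cannot act before 72 patients. Under the assumptions listed in the working, the planned start costs between about 2 additional 5-day-arm patients (true rate 20%, compared with a start at 24 per arm) and about 12 (true rate 35%, compared with 18 per arm), and up to 14 at 40%. The plan states no expected size of harm. The nearest thing is the mean of the 5-day prior, 0.2/(0.2 + 0.8) = 20%, which carries one patient's worth of information. A reader who takes it at face value should use the smallest savings, about 2 to 3.5 patients. The 138 v 142 discrepancy in total sample size does not affect the conclusion.

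**What to change.** Evaluate the same rule, with the same priors and threshold, every 12 patients from the 48th (24 per arm) or from the 36th (18 per arm). This adds two looks (48, 60) or three (36, 48, 60) before the existing one at 72. Report the result to the DSMC at its quarterly meetings; 142 patients over 12 quarters is about 12 per quarter if accrual is even, so the two schedules roughly match. Leave the efficacy interim and its bounds of 0.00506 and 0.04553 as they are.

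Define the readmission window and include at each look only patients who have completed it. Section 7.2 gives none: the interim is triggered by follow-up for the primary outcome, section 3.1 runs participation to the first postoperative visit, and section 8.1 runs adverse event reporting to 90 days.

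The cost is a few more posterior calculations on data already collected, a false-stop chance at 15% v 15% of about 3% (from 24 per arm) or 4% (from 18) in place of 2%, and a stop chance at 20% v 15% of about 17% or 18% in place of 14%. State these operating characteristics in section 7.2 so that the choice of start is explicit.

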**7.3 Subject Population(s) for Analysis**

**Primary Analysis Population:** All randomized patients will be analyzed as randomized in an intention to treat manner. We expect length of stay to be complete for all patients. Any subjects missing length of stay data will be excluded from all analyses. Subjects without data for a particular secondary outcome will be excluded from the analysis of that outcome.

As-treated Population: Supplemental analysis may be considered analyzing patients “as-treated” if it is determined that more than 5% of subjects were not treated as randomized.

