### **3.2 Primary Study Endpoints**

**Primary endpoint:** Post-operative length of stay (proportion of patients discharged by POD 5)

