#### 4.5.2 Data Collection and Follow-up for Withdrawn Subjects

Data will be used for the purposes of the observation portion of the study up to the point of their withdrawal, any subsequent data will not be collected.

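### The rule in section 7.3 that drops anyone with missing length of stay from all analyses deletes known non-events on the primary endpoint and recorded complications, against the plan's own intention-to-treat statement

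*Combined protocol and SAP*

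**What the plan says.** Section 7.3 sets the analysis population: "All randomized patients will be analyzed as randomized in an intention to treat manner". It adds "We expect length of stay to be complete for all patients" and then gives the rule at issue: "Any subjects missing length of stay data will be excluded from all analyses". The next sentence treats missing secondary outcomes more narrowly: "Subjects without data for a particular secondary outcome will be excluded from the analysis of that outcome".

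Section 3.2 defines the primary endpoint as the proportion discharged by POD 5. Sections 7.1 and 7.2 speak of discharge on that day, but a patient still in hospital after POD 5 is a non-event under either wording.

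For withdrawn subjects, section 4.5.2 says "Data will be used for the purposes of the observation portion of the study up to the point of their withdrawal", and that "any subsequent data will not be collected".

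Under Safety in section 7.2: "The primary safety outcome is hospital readmission". No separate safety population is defined, so the words about all analyses also cover complications and readmission.

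**The concern.** The exclusion depends on the wrong variable. It asks whether total length of stay is recorded, whereas the primary endpoint needs only the patient's status at the end of POD 5. In one group of patients the two differ: those who leave data collection while in hospital after POD 5. Each is a known non-event, and the rule deletes it.

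Two things are at stake. First, the denominator of the primary comparison loses patients who are all failures on the endpoint, so the proportion in the affected arm is overstated. The trial is unblinded, so withdrawal could differ by arm. Second, complications recorded before withdrawal leave the secondary comparisons, although the primary objective in section 2.1 is a shorter stay without an increase in complications. A patient with a long, complicated stay who withdraws is one whose complications should be counted.

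**Working it through.** **1. The plan's own figures.** Inputs from sections 7.1 and 7.2: 71 per arm, rates 0.10 and 0.30, two-sided Fisher's exact test, interim at 72 patients (36 per arm), bounds 0.00506 and 0.04553. Exact enumeration of the two-stage test gives power 80.3% (stated 80%) and early stopping 16.3% (stated 16.2%). Both reproduce. The design allows nothing for missing data, in line with the expectation of complete length of stay.

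**2. Who is affected.**

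| Patient | Length of stay | POD 5 status | Effect of the 7.3 rule |
|---|---|---|---|
| Withdraws in hospital after POD 5 | Not collected (4.5.2) | Known: not discharged | Known non-event and recorded complications deleted |
| Withdraws in hospital before the end of POD 5 | Not collected | Unknown | Recorded complications deleted; primary outcome truly missing |
| Dies in hospital | Coding not stated | Not addressed | Cannot be determined from the documents |
| Discharged, later readmitted | Nearly always known | Known | Stays in |

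Only the first row loses a known primary outcome. The first two rows lose complication data.

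**3. Size on the proportion.** The documents give no count of missing lengths of stay, so the number dropped, d, is an assumption (2 to 7 of 71 in one arm). If all d are known non-events, the expected proportion becomes 71 × rate / (71 − d).

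- Pathway arm, 0.30 × 71 = 21.3 events: d = 2 gives 21.3/69 = 0.309; d = 4 gives 21.3/67 = 0.318; d = 7 gives 21.3/64 = 0.333.
- Control arm, 0.10 × 71 = 7.1 events: d = 2 gives 7.1/69 = 0.103; d = 4 gives 7.1/67 = 0.106; d = 7 gives 7.1/64 = 0.111.

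Losses in the pathway arm widen the difference and losses in the control arm narrow it. At the planning rates more control patients are still in hospital after POD 5 (0.90 × 71 = 63.9 against 0.70 × 71 = 49.7), so the direction cannot be presumed.

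**4. Size on the error rate.** With a true rate of 0.10 in both arms and d known non-events removed from the pathway arm only, the exact rejection rate at the final look goes from 2.0% (d = 0) to 3.3% (d = 2 or 4), 3.4% (d = 7) and 4.1% (d = 10). It stays under 5% because Fisher's test is conservative here. Part of the first step comes from unequal arms, as the next item shows.

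**5. Why single-patient changes in p do not measure the bias.** Take 8 control and 18 pathway discharges, final bound 0.04553.

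| Control | Pathway | Two-sided p | What changed |
|---|---|---|---|
| 8/71 | 18/71 | 0.0494 | Nothing |
| 8/71 | 18/70 | 0.0312 | One pathway non-event dropped |
| 8/71 | 18/69 | 0.0300 | A second dropped |
| 8/72 | 18/71 | 0.0315 | Nobody dropped; one control non-event added |
| 8/70 | 18/70 | 0.0491 | One dropped from each arm |

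The one-sided p moves only from 0.0247 to 0.0224 when the first pathway patient is dropped. With 71 in each arm the mirror-image table counts in the opposite tail, so p = 0.0247 + 0.0247 = 0.0494. With 71 and 70 it no longer does, and the opposite tail shrinks to 0.0312 − 0.0224 = 0.0088. The drop below the bound is therefore mainly the loss of exactly equal arms.

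**The case against.** The strongest reply is that the rule will hardly ever act. This is a single-centre inpatient study, discharge dates stand in hospital records, and the plan says it expects complete data. Section 4.5.1 describes withdrawal only as the subject's own request, and nothing says that leaving the pathway means leaving the study. That stands as to size. It does not defend the sentence: with nothing missing the rule is idle, and with something missing it discards known outcomes.

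A reader might go further in four ways that the documents do not support.

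- **That readmissions vanish from the safety comparison.** A readmitted patient was first discharged, so length of stay is nearly always known. A patient who withdraws in hospital has no later readmission data under 4.5.2 and would leave that analysis anyway under the outcome-specific rule.
- **That everyone dropped is a failure on the primary endpoint.** Withdrawal before the end of POD 5 leaves the status unknown, and a missing discharge date may do so too.
- **That in-hospital deaths are excluded.** The documents do not say how a death is coded for length of stay. That is an unstated detail, not a proven exclusion.
- **That one dropped patient flips the verdict, which would show serious bias.** The p-values are correct, but the jump mainly reflects unequal arms. If exactly one pathway non-event is assumed dropped, the final-look verdict changes in 4.9% of trials at 10% against 30% and in 0.8% under the null, and these figures carry the same artefact.

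**Conclusion.** The exclusion sentence in section 7.3 is wrong as written. It contradicts the intention-to-treat sentence before it, is broader than the outcome-specific rule after it, and deletes data that section 4.5.2 keeps. What is lost is known non-events on the primary endpoint and complications recorded before withdrawal.

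The likely size is small. Two to four such patients in the pathway arm alone would move its expected proportion from 0.300 to between 0.309 and 0.318. These counts are assumptions, as is the confinement to one arm. This is a faulty rule, not a demonstrated bias, and its direction depends on which arm loses patients. Readmission is affected minimally.

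**What to change.** Replace the exclusion sentence in section 7.3 with rules to this effect:

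- The primary analysis includes every randomized patient whose POD 5 status is known, in the arm assigned. Anyone known to be still in hospital at the end of POD 5 counts as not discharged by POD 5, whether or not total length of stay is recorded.
- Missing length of stay excludes a patient only from the length-of-stay analysis.
- Complications and readmission are each analysed in all patients with data on that outcome.
- Patients with unknown POD 5 status are reported by arm, with a simple sensitivity analysis of the primary result.

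The same edit could state how an in-hospital death is recorded for length of stay. A compulsory imputation for unknown status, or new consent wording, goes beyond what this defect requires.

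The cost is a few sentences in one section and one small extra analysis. Sample size, test and stopping bounds stay as they are: 71 per arm, with power of 80.3% when no POD 5 status is missing.
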